#### 15.2.5.1 Extent of Exposure

Exposure to IMP will be confirmed based on the report of IMP vials returned and dosing recorded in the clinical database.

#### 15.2.5.2 Adverse Events

Adverse events (AEs) will be coded using the Medical Dictionary for Regulatory Activities (MedDRA). Events will be identified as treatment-emergent (TEAE) and non-treatment-emergent (Non-TEAE) on the basis of the date of onset relative to the date of randomization.

Summaries (number and percentage of events as well as of patients with any events of a particular type) of treatment-emergent AEs (by system organ class and preferred term) will be provided. Number (%) of patients experiencing TEAEs by severity, relationship to IMP, seriousness, and action taken with regard to IMP will be summarized. Number (%) of patients with TEAEs leading to discontinuation of clinical trial participation will also be summarized.

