#### 13.1.1 Adverse Events (AEs)

#### 13.1.1.1 Definitions

Adverse Event (AE)

An AE is any untoward medical occurrence in a patient after administration of a pharmaceutical product and which does not necessarily have a causal relationship with this treatment. An AE can therefore be any unfavorable and unintended sign (including an abnormal laboratory finding), symptom, or disease temporally associated with the use of a medicinal (investigational) product, whether or not related to the medicinal (investigational) product (ICH Guidelines for Good Clinical Practice, E6(R2), 9 November 2016).

This includes worsening of a pre-existing condition or increase in frequency of a pre-existing condition. An adverse event is considered serious if it meets any of the serious criteria listed below. To ensure no confusion or misunderstanding of the difference between the terms "serious" and "severe", which are not synonymous, the following clarification is provided:

The term "severe" is often used to describe the intensity (severity) of a specific event (as in mild, moderate, or severe myocardial infarction); the event itself, however, may be of relatively minor medical significance (such as severe headache). This is not the same as "serious", which is based on patient/event outcome or action criteria usually associated with events that pose a threat to a patient's life or functioning. Seriousness (not severity) serves a guide for defining regulatory reporting obligations.

The official definition also extends to AEs occurring during the off-treatment follow-up period.

Each patient will be closely observed and questioned for AEs during the clinical trial period with non-leading questions (e.g., how do you feel?). The patients will be instructed to report to the clinical trial staff immediately any symptoms and/or signs which occur between the scheduled observation times.

All AEs reported by the patient or observed by the Investigator or hospital personnel will be documented in the respective eCRF. The following information regarding each adverse event will be obtained: date and time of onset and resolution (duration), serious or non-serious (as defined below), severity, treatment required, outcome, relationship to certain medication, and if the AE caused withdrawal from the clinical trial.

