#### 14.2.2 Visit 1 / Baseline Visit

Baseline Prior to Start of Treatment

- Verify Informed Consent was obtained
- Verify Demographics/Medical History
- Verify Inclusion/Exclusion Criteria were met at the Screening Visit
- Repeat Serum (or Urine) Pregnancy Test, if result was obtained more than 7 days prior to the visit
- Physical examination
- Vital signs
- Clinical laboratory tests. Not mandatory in case laboratory tests at screening visit have been performed within 2 weeks from Visit 1
- CCI CCI Patients will be provided with the portable spirometer at the Visit 1 / Baseline Visit only if the patient will be randomized in the study
- Randomization
- Blood sampling for serum levels of calcineurin inhibitors and mTor inhibitors

- Concomitant medications/therapies
- Adverse events
- EQ-5D-5L Questionnaire

Start of Treatment

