### 9.3 Study Day and Time from Randomization

Study Day 1 is defined to be the day of the randomization visit (visit 1, week 0). Time from randomization (in days) for subsequent visits is defined to be visit date – date of randomization visit +1.

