#### 13 Prior and concomitant medications

Prior medications are those medications taken prior to randomization with a stop date and time prior to the randomization date/time (standard definition of prior/concomitant medications considers the first dose of study treatment but, as in this study SOC group won't have any first dose date, randomization date will be considered instead).

Concomitant medications are those medications with a start date and time on or after the randomization date/time, or those with a start date and time before the randomization date/time

Final Version 5.0 Page 37 of 76

and either a stop date and time on or after the study randomization or are ongoing at the end of the study.

Prior and concomitant medications will be summarized by ATC codes and listed for FAS. Prior/concomitant medications will be coded using the WHO-DD classification system and grouped by drug class and PT.

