#### 15.3 Adverse Events

All AEs occurring during the clinical trial, whether or not attributable to study treatment, will be documented in the eCRF. All AEs will be coded to SOCs and PTs using the MedDRA dictionary (version 23.1).

Treatment-emergent adverse events (TEAEs) are defined as AEs with onset on or after the date of randomization.

The Investigator will assess the relationship (unrelated, possible, definite) of each AE to the clinical trial treatment assignment (L-CsA plus SoC or SoC alone). Treatment-related AEs are defined as events the Investigator considers to be possibly or definitely related to clinical trial treatment assignment.

All AEs reported in the eCRF will be presented in by-patient listings for the SAF.

The following summaries will be presented for AEs by treatment group and overall:

- Overview table including the number and percent of patients with:
  - o AEs,
  - o TEAEs.
  - o TEAEs leading to discontinuation of study treatment,
  - o TEAEs leading study discontinuation,

Final Version 5.0 Page 61 of 76

- o TEAEs leading to death.
- o TEAEs by severity (Mild, Moderate, Severe),
- o Study treatment related TEAEs,
- o Serious TEAEs,
- Serious study treatment related TEAEs;
- TEAEs, grouped within SOC by decreasing frequency of PT;
- TEAEs by decreasing frequency of PT;
- TEAEs leading to discontinuation of study treatment, grouped within SOC by decreasing frequency of PT;
- TEAEs leading to study discontinuation, grouped within SOC by decreasing frequency of PT;
- TEAEs leading to death, grouped within SOC by decreasing frequency of PT;
- TEAEs by maximum severity, grouped within SOC by decreasing frequency of PT;
- TEAEs by relationship, grouped within SOC by decreasing frequency of PT;
- Serious TEAEs, grouped within SOC by decreasing frequency of PT;
- Related serious TEAEs, grouped within SOC by decreasing frequency of PT.

Patients who have multiple events coded to the same PT or within the same SOC will be counted only once in the patient counts for the corresponding summaries, but all events will be considered and listed. Table presentations will contain counts of patients, percentages of patients, and the number of events.

Any AE with missing relationship will be assumed related and summarized in the possible related category to clinical trial treatment assignment. Patients who experience the same event multiple times will be included in the most related category for summarization.

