## 15.4 Acute Tolerability of IMP

At Visit 1, acute tolerability of IMP (L-CsA) during initial dosing will be determined by measuring:

- Spirometry (FEV1, CCI , FVC) measured before and CCI
- Spontaneous report of cough or dyspnea, recorded as AE in the appropriate eCRF.

Descriptive statistics of pre-dose (V1), post-dose [CC] and and change from pre-dose will be presented for each spirometry parameter on the SAF population.

In addition, the number and percent of patients experiencing a decline of common in FEV1 will be presented.

Final Version 5.0 Page 63 of 76

The number and percent of patients experiencing new onset or worsening of TEAEs having the following PTs on the date of the first visit at which L-CsA is administered will be summarized:

- Cough;
- Dyspnea.

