#### **Biochemistry**

- Alkaline phosphatase (AP),
- Alanine aminotransferase (ALT),
- Aspartate aminotransferase (AST),
- Gamma Glutamyl Transferase (γ-GT),
- Blood urea nitrogen (BUN),
- Serum bilirubin,
- Serum creatinine,
- Sodium,
- Potassium,
- Chloride,

Final Version 5.0 Page 64 of 76

- Bicarbonate,
- Calcium,
- Magnesium.

Descriptive statistics of observed values and changes from baseline will be presented by visit and treatment group. The summaries described in this section will be presented relative to baseline, defined as the most recent, non-missing result on or before the date of randomization. No imputation for missing data will be performed.

All clinical laboratory data reported in the eCRF will be presented in by-patient listings.

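### SAP 15.4 counts cough and dyspnea by calendar date, so events that began before the first L-CsA inhalation enter the acute tolerability summary; the TEAE rule in SAP 15.3 has the same gap, with little effect

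*Protocol*

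**What the plan says.** Protocol 15.2.5.2 classes adverse events "on the basis of the date of onset relative to the date of randomization". That sentence does not say where an event on the randomization date itself belongs. SAP 15.3 does: "Treatment-emergent adverse events (TEAEs) are defined as AEs with onset on or after the date of randomization". No clock time is used.

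SAP 15.4, on acute tolerability, counts patients with new onset or worsening of cough or dyspnea TEAEs "on the date of the first visit at which L-CsA is administered will be summarized". The spirometry part of the same section is set up differently, as change from a pre-dose value.

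SAP 9.3 makes the randomization visit Study Day 1. Protocol 14.2.2 lists the Visit 1 examination, vital signs and laboratory tests, then randomization, under "Baseline Prior to Start of Treatment". The supervised first inhalation follows at the same visit.

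Other provisions handle timing more finely or set a different scope:
- Protocol 13.1.1.1 has sites record the time as well as the date of AE onset, and SAP 15.3 puts start time in the AE listings.
- SAP 13 defines concomitant medications as "those medications with a start date and time on or after the randomization date/time" (or ongoing from before).
- SAP 9.5.3.2 imputes incomplete AE start times against the date and time of randomization.
- SAP 9.4 separates spirometry done before IMP inhalation from spirometry done after it.
- SAP 9.2.1 and Protocol 15.1 limit the safety summaries to data collected after baseline.
- SAP 15.5.1 takes as laboratory baseline the latest result up to and including the randomization date.

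**The concern.** Acute tolerability of the IMP is a listed safety endpoint (Protocol 9.1, SAP 7.6). Its symptom count should describe what followed the first inhalation. As written it covers the whole calendar day, including the hours of baseline assessment, randomization and device training before any drug was inhaled. The count is tied to L-CsA administration, so the SoC arm supplies no background rate against which a reader could discount pre-dose events.

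The TEAE rule has the same gap. Medical history closes at consent (Protocol 14.2.1), so a condition starting between consent and randomization is an AE. If its onset is dated Visit 1 but precedes randomization, SAP 15.3 makes it treatment-emergent. That sits badly with the after-baseline scope in SAP 9.2.1 and with the date-and-time rules in SAP 9.5.3.2 and 13.

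**Working it through.** The plan states no figure on this point, so there is none to reproduce. The check has two steps.

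**Step 1: apply the written rules to the Visit 1 sequence (L-CsA patient).**

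| Event | TEAE (SAP 15.3) | Acute count (SAP 15.4) |
|---|---|---|
| Onset before the Visit 1 date, only noticed at Visit 1 | No | No |
| Cough ongoing from before Visit 1, not worsened | No | No |
| New or worse cough on the Visit 1 date, before randomization | Yes | Yes |
| New or worse cough between randomization and first inhalation | Yes | Yes |
| New or worse cough that day, after first inhalation | Yes | Yes |

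The third row is misclassified in both summaries. The fourth row is correctly a TEAE, because the plan's reference point is randomization, but is wrong in the acute count. Correcting SAP 15.3 alone would therefore not repair SAP 15.4.

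**Step 2: size, under assumed rates.** The documents give no AE counts. Let p be the true risk after the reference time and q the risk of a counted same-day event before it. If the two are independent, reported risk = 1 − (1 − p)(1 − q).

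*Acute count.* SAP 8.2 gives 169 randomized, 1:1, so 169/2 ≈ 85 on L-CsA, taking all as dosed. One patient counted only for a pre-dose event adds 1/85 ≈ 1.2 percentage points. With p = 5% assumed (85 × 0.05 ≈ 4 patients):
- q = 0.07%: 1 − 0.95 × 0.9993 = 5.07%
- q = 1%: 1 − 0.95 × 0.99 = 5.95%
- q = 3%: 1 − 0.95 × 0.97 = 7.85%, about 1.6 times the true value

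*General TEAE tables.* For a background rate, spread an assumed 20% risk evenly over the 337 days to Week 48: −ln(0.80)/337 ≈ 0.07% per day. With q = 0.07% in both arms:
- p = 20%: 1 − 0.80 × 0.9993 = 20.06%
- p = 10%: 1 − 0.90 × 0.9993 = 10.06%
- ratio 20.06/10.06 = 1.99, against a true 2.00

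**The case against.** Three stronger readings are tempting, and the documents do not support them.

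- **A reader might infer that anything found at Visit 1 becomes treatment-emergent.** The rule turns on onset, not detection. The laboratory case, where one Visit 1 sample is both baseline (SAP 15.5.1) and the source of a TEAE, is narrow. Visit 1 laboratory tests are optional if screening tests fall within 2 weeks, an abnormal result is an AE only if it indicates a clinical condition meeting the AE criteria, and onset must also be dated that day.
- **A reader might infer that pre-dose cough is classed as L-CsA intolerance.** Protocol 10.3.1.1 defines intolerability as an FEV1 reduction together with respiratory symptoms. Cough alone does not meet it. SAP 15.4 is a descriptive count.
- **A reader might infer marked dilution of TEAE comparisons.** If 5% of each arm had a same-day event before randomization, 20% vs 10% would be reported as 1 − 0.80 × 0.95 = 24.0% vs 1 − 0.90 × 0.95 = 14.5%, ratio 1.66. Nothing in the documents supports 5% within a few hours, and much the same assessments were done at screening at most 4 weeks earlier.

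The rest of the opposing case is partly right. SAP 15.1 plans no inferential safety analysis, TEAEs are tabulated by relationship, listings show recorded start times, and keeping same-day events is the inclusive choice. SAP 15.4 also speaks of tolerability during initial dosing and relies on spontaneous reports. Spirometry precedes inhalation and Protocol 12.1.1 names cough as a manoeuvre artefact, but no document says that the manoeuvres produce reported cough AEs. If they do, post-dose spirometry could as well, and a timing rule would not remove that cough.

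These points settle that the effect on the TEAE tables is minor. They do not answer the SAP 15.4 gap: the introductory phrase is not carried into the counting rule, and a listing does not correct a table.

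**Conclusion.** The point holds in a limited form. In SAP 15.4, cough or dyspnea that starts or worsens on the first-dose date before the inhalation is counted as acute tolerability of L-CsA, without a control count. The percentage rests on about 85 patients, so two or three such events would add about 2.4 to 3.5 points (2/85, 3/85). How many will occur cannot be derived from the documents; the 5.1% to 7.9% range rests on assumed risks and independence.

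In SAP 15.3 the same-day rule conflicts with SAP 9.2.1, 9.5.3.2 and 13 and should be reconciled with them. Its effect is limited to one day, identical in both arms and close to nil. No efficacy result is touched, and no material change to the overall safety conclusions is shown.

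**What to change.** - **SAP 15.4:** count cough and dyspnea only when the recorded onset date and time is at or after the start of the first L-CsA inhalation.
- **SAP 15.3, with Protocol 15.2.5.2 read accordingly:** where onset time is recorded, define a TEAE as an AE with onset date and time at or after the randomization date and time.
- **Missing times:** a same-day event with no recorded time stays counted in both summaries. This fits SAP 9.5.3.2: if the earliest possible start is taken as midnight, the imputed start is the randomization time.
- **No exemption by source of detection.** The AE fields in Protocol 13.1.1.1 do not record which assessment revealed an event, so an exemption would need case-by-case judgement in an open-label trial.

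The cost is two changed sentences and the matching derivations. Onset time is already collected. Counts may fall slightly, and the result depends on the quality of recorded times. The visible text does not state that the start time of the first inhalation is recorded. If it is missing for a patient, that patient's same-day events should stay in the acute count, with the number of such cases in a footnote.

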#### 9.6 Stopping Rules and Discontinuation Criteria

#### 9.6.1 Patient Level

#### Regular termination of clinical trial participation:

The investigational treatment will be terminated after 48 weeks (End of Treatment [EoT]). The treatment period will be followed by a follow-up of 4 week duration (End of Study [EOS]). Patients who enroll in Clinical Trial BT – L-CsA – 303 – FU (BOSTON-3) will forego the 4-week follow-up period of BOSTON-2 and will enroll directly into BOSTON-3 at the Week 48 Visit. For these patients, the End of Treatment (EoT) visit will be the EOS visit.

Any patients with ongoing SAEs will be followed-up until recovery or stabilization of the SAE. If a patient has enrolled in BOSTON-3, pharmacovigilance will be continuously assessed in the scope of the follow-up clinical trial.

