#### 10.3.3 Follow-up of Withdrawn Patients

Patients stopping to take study treatment but not revoking their consent will be encouraged to continue the visits planned until the scheduled end and perform all the important safety and efficacy assessment for the full duration of the study.

All patients withdrawn from the clinical trial prematurely will be followed for AEs and SAEs for further 4 weeks. Any patient with ongoing SAEs will be followed until recovery or stabilization of the SAE.

The 4-week safety follow-up will be obsolete if a patient completes participation in the clinical trial and consents to participate in Study BT - L-CsA - 303 - FU (BOSTON-3). In this case, safety will be continuously assessed in the scope of the follow-up clinical trial.

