## Safety analysis set (SAFSet)

The SAF is defined as all randomized patients in the SoC group and all randomized patients receiving at least one dose of IMP in the L-CsA plus SoC group. All data collected after baseline to the end of clinical trial participation will be included in the safety summaries. Patients will be analysed according to the treatment they actually received.

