#### 15.3.1 Infections

All infections will be reported as AEs on the AE eCRF. The summaries described in this section will be provided for treatment-emergent infections (defined as for TEAEs). Treatment-emergent infections will be summarized on the basis of information reported on the AE eCRF.

For any infection, the following summaries will be presented by treatment group:

- Number (percent) of patients with at least one infection,
- Number and % of infections per patient (0, 1, 2, ...),
- Descriptive statistics for number of infections per patient.

The number of infections per patient and per patient-years (cumulative follow-up of each patient) will be provided by year (e.g., 2019, 2020, 2021, etc.) and overall.

A by-patient listing summarizing information on infections will be provided on SAF set.

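### Apart from infections, adverse event tables give only counts and percentages although follow-up differs between patients, so unequal withdrawal by arm could create or hide a modest difference

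*Protocol*

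**What the plan says.** - **Measure.** Protocol 15.2.5.2 asks for "Summaries (number and percentage of events as well as of patients with any events of a particular type) of treatment-emergent AEs". SAP 15.3 says: "Table presentations will contain counts of patients, percentages of patients, and the number of events". This covers any TEAE, serious TEAEs, TEAEs leading to death and the tables by system organ class (SOC). SAP 15.3.2 gives malignancies a table by SOC and preferred term. None of these has a person-time denominator.
- **Start and end.** SAP 15.3: "Treatment-emergent adverse events (TEAEs) are defined as AEs with onset on or after the date of randomization". No common end day is set. Protocol 15.1, repeated in SAP 9.2.1, says: "All data collected after baseline to the end of clinical trial participation will be included in the safety summaries".
- **Length of follow-up.** Under Protocol 9.6.1 the 48 treatment weeks are followed by 4 more, but patients entering BOSTON-3 "will forego the 4-week follow-up period of BOSTON-2 and will enroll directly into BOSTON-3 at the Week 48 Visit". Protocol 10.3.3 confirms this ("The 4-week safety follow-up will be obsolete if a patient completes participation in the clinical trial and consents to participate") and gives patients who leave the trial early 4 further weeks of AE and SAE follow-up.
- **Exception.** SAP 15.3.1: "The number of infections per patient and per patient-years (cumulative follow-up of each patient) will be provided by year", and also overall.
- **Related tables.** SAP 15.2.2 summarizes each patient's time from randomization to completion or early termination. SAP 10 tabulates disposition by arm.

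**The concern.** A percentage of patients with an event, or a raw event count, compares arms fairly only if both arms are observed for about the same time. Here the observation time depends on two decisions made after randomization by people who know the allocation: leaving the trial and entering BOSTON-3. The incentives differ. For an SoC patient, BOSTON-3 means starting L-CsA; for an L-CsA patient, it means continuing. Only the L-CsA arm can find an inhaled study drug intolerable. Protocol 13.2 has the DMC compare withdrawal between arms, so an imbalance is treated as possible.

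The arm that loses more patients early collects fewer events and looks safer. This touches the serious TEAE and death comparisons, and safety is half of the trial objective. The SAP already accepts patient-year rates for infections, so the gap is one of coverage.

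**Working it through.** The plan states no figure for AE risk, withdrawal by arm or roll-over, so there is nothing to reproduce. Two figures give loose orientation. Protocol 15.5 goes from 100 to 110 patients, an allowance of 1 - 100/110 = 9.1%. SAP 8.3.3 reports pooled completion above 67% at the interim analysis, but that concerns FEV1 data by visit and is only a rough upper guide to withdrawal.

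**Inputs from the documents:** follow-up of 48 weeks (enters BOSTON-3) or 52 weeks (does not); time to withdrawal plus 4 weeks (withdraws).

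**Assumptions:** the same constant hazard in both arms, with 40% having an event by Week 48; withdrawal of 25% on L-CsA v 10% on SoC (also 15% v 5%); 10% of completers not rolling over.

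**1. Risk by length of follow-up.** h = -ln(0.60)/48 = 0.01064 per week and P(T) = 1 - exp(-hT).
- P(16) = 15.7%, P(48) = 40.0%, P(52) = 42.5%.
- Completers: 0.9 × 40.0 + 0.1 × 42.5 = 40.25%.
- Withdrawal uniform over 48 weeks plus 4 weeks: 1 - [exp(-4h) - exp(-52h)]/(48h) = 25.0%.

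**2. Percentage with an event, equal true hazards**

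| Withdrawn, L-CsA v SoC | Observation of withdrawn patients | L-CsA | SoC | Difference |
|---|---|---|---|---|
| 25% v 10% | uniform + 4 weeks | 0.25 × 25.0 + 0.75 × 40.25 = 36.4% | 0.10 × 25.0 + 0.90 × 40.25 = 38.7% | -2.3 pp |
| 15% v 5% | uniform + 4 weeks | 38.0% | 39.5% | -1.5 pp |
| 25% v 10% | 16 weeks for all | 34.1% | 37.8% | -3.7 pp |
| 15% v 5% | 16 weeks for all | 36.6% | 39.0% | -2.5 pp |

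Swapping the shares between arms reverses the sign.

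**3. Event counts.** Under uniform withdrawal plus 4 weeks the withdrawn average 28 weeks and completers 48.4. Mean follow-up at 25% v 10% is 0.25 × 28 + 0.75 × 48.4 = 43.3 weeks v 0.10 × 28 + 0.90 × 48.4 = 46.4 weeks. The raw count ratio is 0.93 although the true rates are equal.

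**4. Roll-over alone.** With no withdrawal and 30% v 10% not rolling over: (0.30 - 0.10) × (42.5 - 40.0) = 0.5 pp. The ceiling on event counts is 52/48 = 1.083, reached only if one arm rolls over entirely and the other not at all.

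**5. Masking.** A true hazard ratio of 1.2 gives 1 - 0.60^1.2 = 45.8% v 40.0% with full 48-week follow-up, a difference of 5.8 pp. With 25% v 10% withdrawn, uniform plus 4 weeks, the same formulas give 41.8% v 38.7%, or 3.1 pp. With 16 weeks for all withdrawals and no weeks after Visit 9, they give 39.0% v 37.6%, or 1.4 pp.

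**6. With person-time.** Expected events are h × T over person-time T, so equal hazards give a rate ratio of 1.00 in every row above.

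**The case against.** - **Only part of the variation is by design.** The 48 v 52 week rule applies to both arms and is worth about 0.5 pp. A reader might infer that the design itself biases the comparison. It does not: bias needs roll-over or withdrawal to differ by arm, and nothing in the documents shows that. This stands.
- **The larger figures depend on a harsh input.** Observing every withdrawal for only 16 weeks leaves little room for the 4-week AE follow-up in Protocol 10.3.3. A reader might take -3.7 pp as the expected size; it is an upper case, and -2.3 pp fits the protocol better. This stands.
- **Mitigations exist.** Patients who stop treatment are encouraged to stay for all visits (Protocol 10.3.1, 10.3.3), and disposition and duration are shown by arm (SAP 10, 15.2.2). A reader could see an imbalance, but no AE table corrects for it. Consent withdrawal, re-transplantation and loss to follow-up still end participation.
- **Infections are covered.** It would be too broad to say that no AE summary uses person-time.
- **The weeks after Week 48 are not simply off-treatment.** That reading fails for the control arm, because SAP 15.2.2 runs SoC to study completion.
- **Sampling noise is larger.** With 169 randomized (SAP 8.2), about 84 per arm, the 95% margin on a difference near 36% is 1.96 × sqrt(2 × 0.36 × 0.64/84.5), about 14 pp, and SAP 15.1 plans no safety inference. This limits the importance. But the distortion is systematic, readers compare the columns anyway, and Protocol 15.2.5 allows tests and confidence intervals where applicable.

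**Conclusion.** The point holds in a limited form. The TEAE, serious TEAE, TEAE-leading-to-death and malignancy tables have no person-time denominator, while follow-up runs to each patient's own end of participation. If withdrawal differs by arm, raw percentages can mislead modestly: about -2.3 pp, at most -3.7 pp in the cases examined, for 25% v 10% withdrawn at a 40% risk. Unequal roll-over is a minor contributor. The withdrawal and roll-over shares, the event risk and the constant hazard are assumptions, and the documents give no evidence that the arms differ. The primary efficacy analysis is not affected. The change is worth making because it is cheap, and it should be settled before results by arm are seen.

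**What to change.** In SAP 15.3 and 15.3.2, for any TEAE, serious TEAEs, TEAEs leading to death, malignancies and each SOC, add by arm beside n (%):

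1. Events per 100 patient-years, with patient-years over exactly the window in which events are counted: randomization to the end of AE observation, including the 4 weeks after withdrawal.
2. Patients with a first event per 100 patient-years at risk, with each patient's time censored at the first event.

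Keep the rule in Protocol 15.1 and SAP 9.2.1 that all data to the end of participation are included. If a table cut at Visit 9/EoT is also shown, end its person-time on the same date. Pairing such a table with the SAP 15.2.2 duration, which runs to study completion, would be wrong: with equal rates and 30% v 10% not rolling over, the false rate ratio is 48.4/49.2 = 0.98, and 48/52 = 0.92 at the extreme. For the same reason the 15.2.2 duration cannot serve for first-event rates.

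The cost is SAP wording and a few extra table columns, with no new data. The rates correct for unequal observation time only; they do not correct for sicker or healthier patients being the ones who leave.
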